4.4 Randomization

Subjects will be randomly assigned to either the CTPA group or the VQ group (1:1 ratio) using a computer generated randomization list with a block size of 4. Assignment will utilize REDCap (Research Electronic Data Capture, hosted by Indiana CTSI, <https://redcap.uits.iu.edu/>), a secure web-based application that will automate a separate, computer based randomization list for each enrollment site, generated by the biostatistician ([name]). To balance in the risk of PE, we will use the PE PreTest Consult Score as a stratification factor (a <10% risk group and a 10-20% risk group).

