Safety Endpoints	
Defined as one or more of the following events occurring within 7 days (168 hours) of the enrollment PE imaging study:
 
 1) Time to treatment of PE > 8 hours defined as the time from study enrollment until initiation of anticoagulant therapy for PE. 2) Complications of PE imaging defined as one or more of the following occurring within 24 hours of the enrollment imaging study and requiring medical or surgical intervention: hypotension, difficulty breathing, acute pulmonary edema or hypervolemia, oral swelling, rash or puritis, abdominal pain, nausea or vomiting, altered mental status, or soft tissue contrast media or radio-isotope extravasation.

	
3) Severe health outcomes defined as one or more of the following occurring within 168 hours of the enrollment imaging study: AKI (Acute Kidney Injury Network [AKIN] 1-3); Death (any cause), renal failure, or one or more of the following requiring medical or surgical intervention: acute myocardial infarction, stroke and/or other acute arterial vascular event, in any anatomic distribution, requiring medical or surgical intervention; death with renal injury as a significant contributor defined as obvious evidence of renal failure defined by worsening azotemia with complications of renal failure including oliguria, pulmonary edema, hyperkalemia, pericardial effusion, or the need to initiate renal replacement therapy before death; identification of a venous thromboembolism (VTE, PE and/or DVT) requiring medical or surgical intervention; death from VTE and/or hemorrhage requiring medical or surgical intervention as a result of treatment for VTE.

Tertiary End-points	Mid- (occurring within 30 days) and Long-term (occurring within 1 year) severe health outcomes
Number of Subjects	
 • A total of 700 subjects will be enrolled inclusive of 600 subjects that will be randomized to CTPA or VQ imaging and 100 non-randomized subjects that will undergo CTPA.
Inclusion Criteria	
 1) Age ≥ 18 years CTPA ordered by the treating provider to evaluate PE. 2) Pre-test probability of PE $\leq 20\%$ defined using the PE Pretest Consult Score. 3) For randomization to CTPA or VQ imaging (600 subjects): AKI risk $\geq 20\%$ assessed by an AKIrisk Score ≥ 2 points 1) For non-randomized CTPA group (100 subjects): AKI risk $< 10\%$ assessed by an AKIrisk Score < 2 points.

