3.2 Number of Study Sites

The study will be conducted at 5 emergency care sites: IUH Methodist Hospital (also provides emergency care services for IUH University Hospital), Eskenazi Health Hospital, IUH Ball Memorial Hospital, University of Utah, and Intermountain Healthcare.

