4.3 Exclusion Criteria

- 1) History of pulmonary surgery or findings on chest-radiograph that may limit the accuracy of VQ imaging for the detection of PE including air-space disease occupying more than 50% of the lung field, significant mass, or pleural effusion of significant volume or associated with low-lobe air-space disease.
- 2) Clinical instability or other condition preventing randomization to CTPA or VQ imaging.
- 3) Pregnancy or ≤48 hours post-partum.
- 4) Subject unavailability for reasonable follow-up including biological sample collection, creatinine measurement, and interview, such as an insecure residence, planned travel or absence, personal or professional obligations, incarceration, and/or other reason preventing follow-up, identified at enrollment.
- 5) Active renal replacement therapy (hemodialysis or peritoneal dialysis) within 30-days of enrollment or previous physician-directed plans to initiate dialysis within 30-days of the index visit.
- 6) Prior renal transplant or planned within 30-days of enrollment.
- 7) Intravascular contrast administration within 14 days prior to enrollment or planned within 7 days of enrollment.

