6.0 Safety Assessment and Reporting

The study coordinators will also communicate closely with the clinical team, inform them of the PE imaging randomization assignment, and assist the clinical team to coordinate the completion of the PE imaging. The study coordinator will notify the treating provider of any conditions that exclude the patient from participation in this study. A study physician will be available by telephone during patient enrollment and the completion of PE imaging. The flowchart shown in appendix 1. describes the study procedures including randomization, assessment of outcomes, and PE imaging completion, including the process for crossover from the VQ arm to CTPA. Patients with suspected DVT will also undergo lower extremity ultrasound (US), at the discretion of the treating provider, as will patients with an intermediate risk VQ. Thus, only patients who, after pre-enrollment screening for non-high risk of PE, appropriateness for VQ imaging, have an intermediate risk VQ study and a negative DVT US, will require crossover to CTPA to exclude PE.

Patients who develop CIN, based on the study definition and follow-up creatinine measurement, will receive a telephone call notifying them of this result. If the patient cannot be reached by telephone, we will also send a letter (paper mail, and if provided, email) informing them of their creatinine measurement. The same notification letter will provide instructions to seek follow-up care with either their primary care physician, or for patients without a primary care physician, with instructions to follow-up in the emergency department.

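### A single block size of 4, printed in the protocol and used in site-by-PE-risk strata with assignments known to recruiting staff, makes up to one third of assignments certain to anyone tracking a stratum

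*Combined protocol and SAP*

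**What the plan says.** Section 4.4 allocates patients 1:1 to CTPA or VQ "using a computer generated randomization list with a block size of 4". REDCap holds "a separate, computer based randomization list for each enrollment site", and the PE PreTest Consult Score is a stratification factor with two levels (below 10%, and 10-20%). No varying size is mentioned, and nothing says that the size is withheld from sites. Section 3.2 states "The study will be conducted at 5 emergency care sites", and the synopsis gives "600 subjects that will be randomized to CTPA or VQ imaging".

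The term open-label does not appear, but the arms are two different scans. Section 6.0 has the study coordinators work with the clinical team, "inform them of the PE imaging randomization assignment", and help get the scan done. Under section 4.1 the coordinator completes the PE pretest score (which fixes the stratum) and the AKIrisk Score, determines eligibility and obtains written consent. One exclusion in section 4.3 is a matter of judgement: "Clinical instability or other condition preventing randomization to CTPA or VQ imaging". The synopsis version adds that the treating provider reports it. Blinding is described only for the physicians who adjudicate secondary outcomes (section 2.2).

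**The concern.** Central assignment through REDCap hides the list, but it cannot stop a person from counting. If the block size is known and fixed, the end of each block can be deduced from the assignments already made in that stratum. The protocol puts the block size, the stratum and past assignments within reach of the staff who decide whom to approach and who is eligible, and they make those decisions before the next assignment is released.

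There is a plausible motive. Section 1.4 says that perceived CIN risk is the main reason physicians choose VQ over CTPA. Staff who expect a VQ slot might be keener to enrol a patient they think has vulnerable kidneys, and less keen when CTPA is expected. The arms would then differ in AKI risk for reasons unrelated to contrast. Section 1.4 justifies the trial by arguing that non-randomized comparisons suffer from exactly this problem.

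**Working it through.** The protocol states no predictability figure, so there is none to reproduce. The inputs are block size 4, ratio 1:1 and a list per site stratified by two PE-risk levels (section 4.4), 5 sites (section 3.2) and 600 randomized (synopsis).

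**Certain assignments.** There are C(4,2) = 6 equally likely blocks. An assignment is certain when the earlier ones in the block leave only one arm.
- AABB and BBAA: positions 3 and 4 are both certain, so 2 × 2 = 4.
- ABAB, ABBA, BAAB and BABA: only position 4 is certain, so 4 × 1 = 4.
- Share = (4 + 4) / (6 × 4) = 8/24 = 33.3%. The eight positions split equally, four per arm.

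**Best guess** (always name the arm with more slots left; toss a coin if tied).
- Position 1: 1/2.
- Position 2: 2/3.
- Position 3: 1/3 × 1 + 2/3 × 1/2 = 2/3.
- Position 4: 1.
- Mean = (1/2 + 2/3 + 2/3 + 1) / 4 = 17/24 = 70.8%.

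**Incomplete last blocks.** Crossing site with PE risk gives 5 × 2 = 10 strata, or 600/10 = 60 patients each if equal. Simulating 600 patients (3,000 runs) gives 32.6% certain over 10 strata (0.326 × 600 ≈ 196 patients) and 33.0% over 4 strata (≈ 198). If PE risk did not split the site lists, the figure would still be about one third.

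**Alternatives.** The fixed sizes are enumerated. The varying sizes are simulated with 60 patients per stratum, sizes drawn with equal probability, and an observer who sees every assignment but knows only the set of possible sizes.

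| Scheme | Certain | Best guess correct |
|---|---|---|
| Fixed 4 (plan) | 33.3% | 70.8% |
| Fixed 6 | 25.0% | 68.3% |
| Fixed 8 | 20.0% | 66.6% |
| Varying 4/6 | 5.6% | 69.0% |
| Varying 4/6/8 | 2.3% | 67.8% |

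**Scale of a possible shift (illustration; the risks are assumed).** One third of 300 VQ slots is 100. If selection raised mean AKI risk in all of those slots from 20% to 25%, the VQ rate would rise by 5 × 100/300 = 1.7 points; from 20% to 30%, by 3.3 points. Selection in fewer slots shifts it proportionally less. The equivalence margin in section 2.1 is 10 points.

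**Direction.** In that example the observed CTPA-minus-VQ difference falls. If contrast truly raises AKI, this favours equivalence. If there is no true effect, it pushes the result away from equivalence. The opposite preference among staff reverses both.

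**The case against.** The figures describe an observer who knows the block size, the stratum and every earlier assignment in it. The documents do not say that any one person has all of this. Section 6.0 refers to coordinators in the plural, section 1.6 gives research assistants limited access, and each site would normally run two interleaved sequences. This stands: one third is an upper bound, and staff who see only part of a stratum can predict less.

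A reader might infer that patients of high renal risk would be kept from contrast by not enrolling them when CTPA is expected. The documents do not support that as the natural route. CTPA must already be ordered (section 4.2), and section 1.7 says that those who decline have CTPA as planned. Leaving such a patient out therefore does not avoid contrast unless the order changes. The more credible route is enrolling such patients mainly when VQ is expected.

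The judgement-based exclusion formally rests on the treating provider's report, and nothing shows that providers follow the sequence. However, the coordinators decide whom to approach and determine eligibility.

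The plan has relevant checks: a review of enrolment against imaging logs after three months (section 4.1), baseline comparisons between arms (section 2.1), a comparison of enrolled patients with eligible decliners (section 2.2), and covariate adjustment in the logistic model (section 2.1). These can detect selection or reduce its effect on measured factors. None examines selection by expected assignment or prevents it. The equivalence test that decides the primary question uses raw proportions; adjustment enters only in the follow-on model.

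**Conclusion.** The point holds as a weakness in allocation concealment that is cheap to close. With a single known block size of 4, up to one third of assignments (8/24, about 196-198 of 600) are certain to a full tracker of a stratum, whose best guess is right 70.8% of the time.

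This rests on two inferences: that staff know the assignments, from the nature of the arms and section 6.0, and that staff know the block size, from its appearance in the protocol. Crossing site with PE risk is the natural reading of section 4.4, but the one-third figure does not depend on it.

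A reader might infer that the trial is biased, or biased towards equivalence. The documents support neither. They show opportunity and a plausible motive, not actual selection, and the direction depends on staff behaviour and on the true effect of contrast.

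**What to change.** For the unused part of each list (all of it if enrolment has not begun), have the biostatistician generate randomly varying block sizes, for example 4, 6 and 8, within each site-by-PE-risk stratum. Remove the size from section 4.4, say there only that permuted blocks of varying size are used, and record the sizes in a document restricted to the statistician. State explicitly that site and PE risk are crossed.

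Under the assumptions above, this nearly removes certain assignments (to about 2%), but skilled guessing remains almost as good (about 68% against 70.8%). The protocol should therefore not claim that assignments become unguessable.

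The cost is a new REDCap list and a slightly larger possible imbalance. An unfinished block can leave a stratum off by at most half its size: 2 patients with blocks of 4, and 4 with blocks of 8. Over 10 strata the extreme case rises from 20 to 40 patients, and only if every stratum stopped at its worst point in the same direction.

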We acknowledge that the primary outcome of CIN is likely to occur in patients that remain asymptomatic, as expected for the first stages of AKI. We do plan to measure and report patient-center, symptomatic, severe outcomes (see *Secondary Endpoints*) occurring within 1-year. Aside from our own preliminary data,^{7,11,20} there are no consistent, published, prospective data, with sufficient long-term follow-up,^{32,45} in the emergency care setting, or other comparable heterogeneous, ambulatory population (pre-exposure renal function ranging from normal to impaired). Moreover, there are no prospective, controlled data, in any setting, that can be used to adequately design (and determine the sample size for) a study primarily aimed at measuring the long-term, severe outcomes subsequent to CIN. Hence, we have focused on the first phase of AKI, CIN, as the primary outcome, and plan to use the data to inform future research quantifying the effect of selected contrast media exposure on the prevention of long-term severe outcomes subsequent to the development of CIN.

To determine sample size, we conservatively estimated an overall AKI rate of <20%. The sample size was determined based on a Chi-square test (two-tailed, 5% type I error). A sample size of 188 in the CTPA group (exposed) and 269 in the VQ group (unexposed) in each group will have 80% power to detect an absolute difference of 10%. Assuming up to 5% screening and randomization failures (patients assigned to VQ, but undergo CTPA imaging) and a 30% dropout rate,^{7,11,20,53,89} we will recruit 300 subjects per group. (nQuery 2014; Statistical Solutions©)

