We will reject the null hypothesis and the two groups, CTPA and VQ, will be considered equivalent if

$$\frac{\hat{P}_1 - \hat{P}_2 - \delta}{\sqrt{\hat{P}_1(1 - \hat{P}_1)/n_1 + \hat{P}_2(1 - \hat{P}_2)/n_2}} < -z_{0.05} \quad \text{and} \quad \frac{\hat{P}_1 - \hat{P}_2 + \delta}{\sqrt{\hat{P}_1(1 - \hat{P}_1)/n_1 + \hat{P}_2(1 - \hat{P}_2)/n_2}} > z_{0.05}$$

If we reject the hypothesis of equivalency, we will conduct an analysis for a superior trial. Hence, for comparison with the dichotomous primary outcome, that is, whether a subject develops AKI at the 2-7 day follow-up, a logistic regression model will be used. Group comparisons will be adjusted for baseline covariates. To validate the decision rule in classifying subjects into a low-risk group we will: 1) Measure the AKI rate in the low-risk group (AKIRisk Score <2) with a desired margin of error. We assumed the upper limit of the one-way 95% confidence interval to be <10%, based on preliminary data, and prior literature.^{6,7} as such, we will compute the one-way 95% confidence interval using a Z test statistic; and 2) Compute sensitivity and specificity of the decision rule.

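### The primary equivalence test is an unadjusted risk difference that leaves out the randomisation strata and the AKIrisk Score; it is valid but gives up a modest amount of precision

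*Combined protocol and SAP*

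**What the plan says.** Section 4.4 (Randomization) allocates 1:1 in blocks of 4 from a separate list for each site, and states that "we will use the PE PreTest Consult Score as a stratification factor", with groups of below 10% and 10-20%. With the five sites of Section 3.2, this makes ten strata.

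Section 2.1 (Primary Outcome Analysis) tests equivalence with two one-sided z statistics. Each uses the crude difference in AKI proportions, the margin of 10 percentage points and the unpooled binomial variance. Neither has a stratum or covariate term. A superiority analysis by logistic regression follows if equivalence is not established, and there the plan says "Group comparisons will be adjusted for baseline covariates". The covariates are not listed and the effect measure is not given. No analysis text names site or PE PreTest group as an analysis factor.

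The sample size text in Section 2.1 reads "The sample size was determined based on a Chi-square test (two-tailed, 5% type I error"), with "A sample size of 188 in the CTPA group (exposed) and 269 in the VQ group (unexposed") giving "80% power to detect an absolute difference of 10" percentage points. On the event rate it says "we conservatively estimated an overall AKI rate of <20"%. Losses are allowed for by "Assuming up to 5% screening and randomization failures" "and a 30% dropout rate", leading to 300 recruited per group.

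**The concern.** A trial that stratifies its randomisation and scores every patient for AKI risk before allocation holds information that can narrow the confidence interval for the treatment difference. The primary test uses none of it. Two consequences follow.

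First, equivalence is harder to demonstrate than it need be. Crude power is well below 80% if the AKI rate is near 20%, so any precision available without further recruitment is useful.

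Second, the two linked primary steps are not tied to one estimand. Equivalence is judged on a risk difference, while the superiority step comes from a logistic model with an unstated effect measure and an open covariate list. The choice of covariates for a primary comparison could then be made after the data are seen.

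**Working it through.** **1. The plan's own sample size.** Arm-specific rates are not given, so 20% versus 10% is assumed. At the ratio 269/188, a two-sided 5% chi-square test with continuity correction and 80% power needs 183/262 if CTPA has the higher rate, or 189/270 if VQ does. Both are within 3% of the stated 188/269. Separately, the uncorrected 1:1 answer for the same rates is 199 per arm, and 199 / (0.95 × 0.70) = 299, which matches the 300 recruited. Going forward, 300 × 0.95 × 0.70 = 199.5, so about 200 evaluable per arm is used below. Results at 188/269 are also given.

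**2. Power of the crude equivalence test.** At a true difference of zero and common AKI rate p:

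- SE = √[p(1−p)(1/n₁ + 1/n₂)]
- Power = 2Φ(0.10/SE − 1.645) − 1

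With p = 0.20 and 200 per arm, SE = √(0.16 × 2/200) = 0.040. Power = 2Φ(2.5 − 1.645) − 1 = 60.8%. At p = 0.15 it is 75.2%. At 188/269 the values are 67.5% (p = 0.20) and 80.7% (p = 0.15).

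**3. Effect of adjustment.** Adjustment for baseline information explaining a share R² of outcome variance multiplies the variance by (1 − R²).

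- *PE PreTest group.* The only proxy in the documents is AKI of 9% with and 8% without VTE (Section 1.5). Taking equal-sized groups, R² = 0.005² / (0.085 × 0.915) ≈ 0.0003. The gain is at most 0.1 point.
- *Site.* No site-level AKI rates are given. Assume five equally spaced sites. A spread of 15-25% gives R² = 0.00125/0.16 ≈ 0.008, and 10-30% gives 0.005/0.16 ≈ 0.03.
- *AKI predictors.* Under a binormal approximation, d = √2 · z(AUROC) and R² = p(1−p)d² / [1 + p(1−p)d²]. The AKIrisk Score's AUROC of 0.74 (Section 1.5) gives d² = 0.828 and R² = 0.132/1.132 = 0.117. Creatinine eGFR at 0.55 gives R² = 0.005.

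| Adjustment, p = 0.20 | R² | Power, 200/200 | Power, 188/269 |
|---|---|---|---|
| None | 0 | 60.8% | 67.5% |
| PE group only | 0.0003 | 60.8% | 67.6% |
| Creatinine eGFR only | 0.005 | 61.1% | 67.9% |
| Site, 15-25% | 0.008 | 61.3% | 68.1% |
| Site, 10-30% | 0.03 | 62.8% | 69.5% |
| Weak AKI predictors | 0.02 | 62.1% | 68.8% |
| Moderate AKI predictors | 0.05 | 64.2% | 70.8% |
| AUROC 0.74, upper bound | 0.117 | 69.0% | 75.1% |

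In sample-size terms, R² of 0.05 is worth 1/0.95, or about 5% more evaluable patients. R² of 0.117 is worth 1/0.883, or about 13% more.

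**4. Simulation check.** Ten strata were used, with blocks of 4 and 2,500 runs per cell. The crude test was compared with a regression-adjusted risk difference at p = 0.20 and 200 per arm. Adjusting for strata alone with a modest site spread gave no gain (60.9% crude, 60.8% adjusted). Adding a weaker predictor moved power from 60.9% to 63.2%, and a stronger one from 62.1% to 69.2%. With the true difference set at the margin, type I error across the cells examined was 0.039 to 0.059 for the crude test and 0.044 to 0.061 for the adjusted test. Simulation error was about 0.004.

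**The case against.** The case for leaving the plan alone is substantial. An unadjusted risk difference is a legitimate and transparent primary analysis, and its type I error is close to nominal. The strata offer almost no precision: the protocol itself holds that PE does not affect AKI risk, and nothing in it suggests large site differences. The AUROC of 0.74 was observed in the cohort from which the score was derived, across all scores, whereas every randomised patient scores at least 2. Adjustment is also partly planned, in the logistic step.

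All of this stands, and it rules out several stronger readings that a reader might infer:

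- *That the crude test is biased or invalid.* It is not. Leaving out stratification factors makes its standard error at most slightly too large.
- *That adjusting for the strata would recover meaningful power.* The table and the simulation show that it would not.
- *That power near 69-70% can be expected.* This needs the unselected-cohort AUROC to hold among patients scoring 2 or more, where discrimination is not reported.
- *That the two primary steps contradict each other because the second yields an odds ratio.* Section 2.1 names no effect measure, and a risk difference can be standardised from a logistic model. This is a gap in specification.
- *That NGAL and Cystatin-C will be available for everyone.* Sections 4.1 and 5.1 make sample collection permissive, so completeness is uncertain. Cystatin-C's AUROC of 0.76 also has a wide interval, 0.56 to 0.95.

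The objection does not remove the point. The AKIrisk Score is determined for eligibility (Section 4.1) and can still range from 2 to 6 among randomised patients, so some prognostic information should be available at no cost.

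**Conclusion.** The point holds as a modest, avoidable loss of efficiency, together with incomplete specification of the superiority step. At 20% AKI and about 200 evaluable per arm, a realistic gain from AKI predictors is about 1 to 3 power points, from about 61% to 62-64%. Site might add 0 to 2 points and the PE stratum about none. The reason to include the strata is consistency with the design; the precision comes mainly from AKI predictors.

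These sizes rest on a true difference of zero, a common AKI rate of 20%, assumed site spreads and an assumed R² of 0.02 to 0.05 in the randomised population. At 15% AKI, crude power is higher (75.2% at 200 per arm, 80.7% at 188/269) and R² of 0.05 adds about 3 points or fewer. Adjustment will not repair the larger, separate matter that the sample size was set for a difference test while the primary test is one of equivalence.

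**What to change.** In Section 2.1, define the primary estimate as a marginal risk difference, standardised from a logistic model containing treatment, site, PE PreTest group and the AKIrisk Score or its components. Then specify:

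- Equivalence: the 90% CI of this estimate lies within ±10 percentage points.
- Superiority step: the 95% CI of the same estimate, so that both steps address one quantity.
- Covariates: fixed before unblinded data are seen. Baseline creatinine is optional and adds little; Cystatin-C should enter only if nearly complete.
- Sensitivity analysis: the crude Wald test as now written.

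The cost is a paragraph of SAP wording and a few lines of code. No additional data, visits or patients are needed.
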